7.2 Study Conduct

7.2.1 *Accrual*

The accrual pattern will be summarized per country, investigational site, and per month for all treated subjects. Informed consent date, first dosing date, country, and investigational site will be presented in a by subject listing of accrual.

7.2.2 *Relevant Protocol Deviations*

Relevant deviations from the study protocol will be summarized and listed by subjects on the population of all treated subjects.

At entrance:

- Subjects with baseline ECOG Performance Status > 2 .
- Subjects with no prior systemic anti-cancer therapy.
- Subjects with no histologically documented stage III or IV melanoma.
- Subjects without measurable disease at baseline.
- Subjects who have not received anti-CTLA-4 therapy or have not progressed on or after anti-CTLA-4 therapy.

On study:

- Subjects receiving concurrent anti-cancer therapy.

Each subject's data will be examined for deviation from protocol criteria (including violation of eligibility criteria, discrepancies between enrolled and treatment received and on-study deviations).

7.3 Study Population

7.3.1 Subject Disposition

Number of subjects enrolled but not treated along with the reason will be tabulated. This analysis will be performed on the enrolled analysis set.

Study participation status including completion and discontinuation of treatment will be reported using the all treated analysis set. Reasons for discontinuation will be summarized and listed.

A subject listing will be provided showing the subject's off study date and reason for going off-study. A subject listing of subjects not treated will also be provided.

7.3.2 Demography and Subject Characteristics

The demographic characteristics, physical measurements, and other baseline characteristics of subjects will be reported using the all treated analysis set, overall and by subpopulations.

The following demographic characteristics, physical measurements, and other baseline characteristics will be summarized. The age of a subject will be defined as the truncated difference in years between the date of the informed consent and the date of birth, plus 1 day (e.g. $((DD/MM/YYYY2 - DD/MM/YYYY1) + 1/365.25) = \text{result in years to 1 decimal place (xx.x)}$).

Frequency and percentage will be reported, unless otherwise noted.

Demographics characteristics:

- Age (< 65; ≥ 65 and < 75; ≥ 75 and < 85; ≥ 65; ≥ 75; ≥ 85; summary statistics) (years)
- Sex (Male, Female)
- Race (White, Black or African American, American Indian or Alaska Native, Asian, Native Hawaiian or Other Pacific Islander, Other, Not Reported)
- Ethnicity (Hispanic/Latino, Not Hispanic/Latino, Not Reported)

Physical measurements summary:

- Baseline weight (summary statistics) (kg)
- Baseline height (summary statistics) (cm)
- Baseline BMI (summary statistics) (kg/m²)
- ECOG Performance Status (0-1, 2, Not Reported)

Other baseline characteristics:

- Subtype of Melanoma (Mucosal, Cutaneous, Acral, Ocular/Uveal, Other)
- BRAF Mutation status (Wild type, Mutant, Not Reported)

- Current disease stage (Stage III, Stage IV, Unknown)
- M-stage at study entry (M0, M1A, M1B, M1C, Unknown)
- Brain metastasis (Yes, No)
- Treatment status of CNS metastasis (Treated, Untreated, Leptomeningeal)
- Number of prior therapies (1, 2, >=3)
- Baseline LDH (<=ULN, >ULN, <=2*ULN, >2*ULN)
- Type of autoimmune disorder (Endocrine, Gastrointestinal, Hepatic, Skin, and Other)
- Condition of autoimmune disorder (Active, Not Active)

A subject listing of demography and subject characteristics will be produced on the all treated analysis set.

A summary of demographic characteristics, physical measurements, and other baseline characteristics will also be presented by baseline LDH, BRAF status, and type of autoimmune disorder.

7.3.3 Medical History

A subject listing of general medical history will be produced for all subjects in the treated analysis set.

7.3.4 Disease Characteristics

The following baseline disease characteristics will be summarized using the all treated analysis set by subpopulations:

- Time (in months) from initial pathological diagnosis to first dose of study therapy (summary statistics)
- Baseline tumor assessments (subjects with at least 1 lesion, site of disease, number of disease sites)
- Baseline BRAF, NRAS and cKIT status

A subject listing will be produced on all treated analysis set.

7.3.5 Prior Therapy

The following information will be summarized using the all treated analysis set by subpopulations:

- Prior maintenance therapy (Yes, No, Not Reported)
- On study line of therapy for advance metastatic disease (Second line, Third line, Other)
- Type of prior systemic therapy received (Chemotherapy, Immunotherapy)
- Prior systemic therapy regimen setting (Adjuvant, Neo-adjuvant, Metastatic)
- Best response to most recent prior systemic therapy regimen (CR or PR, SD, PD, Not Reported)
- Time from completion of most recent prior systemic therapy regimen to enrollment (< 3 months, 3-6 months, > 6 months, Not Reported)

- Time from completion of prior adjuvant/neoadjuvant therapy to enrollment (<6 months, >= 6 months, Not Reported)
- Prior surgery related to cancer (Yes, No)
- Prior Radiotherapy (Yes, No)

A listing will be provided using the all treated analysis set. A separate listing will be created for the prior anti-CTLA-4 therapy.

7.3.6 Baseline Examinations

Subjects with abnormal baseline physical exam result will be tabulated by examination criteria (e.g. neck, cardiovascular) using the all treated analysis set by subpopulations.

A listing will be provided using the all treated set.

7.4 Extent of Exposure

The analyses of study drug exposure will focus on the on-study period. The first dosing day corresponds to the day of first administration of any nivolumab. Throughout this analysis plan, dose level will refer to the actual dose rather than the planned dose.

Nivolumab dose reductions and escalations are not permitted.

The nivolumab dose delay and interruption of a subject will be evaluated.

A dose interruption refers to an interruption of the infusion of nivolumab, whether or not the infusion is resumed. If a subject is unable to start a cycle because of unacceptable toxicity related to nivolumab, therapy may be held for up to 6 weeks.

Dose delay, up to 6 weeks, is also allowed for study drug so toxicities return to ≤ Grade 1 or baseline.

If a cycle is delayed, the reason for the delay will be ascertained from the “dosing changes” section of the dosing CRFs.

7.4.1 Administration of Study Therapy

The following parameters will be summarized using the all treated analysis set by subpopulations:

- Number of doses received (1, 2, 3, 4, >4. Summary statistics)
- Cumulative dose (summary statistics)
The cumulative dose is the sum of the doses (mg/kg) administered to a subject during the treatment period. Dose (mg/kg) is derived based on dose (mg) divided by the most recent body weight (kg) that is collected in the CRF.
- Relative dose intensity (>= 100%, 90% to < 100%, 70% to < 90%, 50% to < 70%, <50%, Not Reported)
The relative dose intensity is derived as :
$$[\text{Cumulative dose (mg/kg)} / ((\text{Last dose date} - \text{Start dose date} + 14) \times 3/14)] \times 100$$
- Duration of therapy (> 3 months, > 6 months, > 9 months, >12 months, summary statistics). A Kaplan-Meier curve will also be presented where the last dose date is the event date for those

subjects who are off study treatment. Median duration of treatment and associated 95% CI will be provided. Subjects who are still on study therapy will be censored on their last dose date.

7.4.2 Interruption or Delay of Study Therapy

The following parameters will be summarized using the all treated analysis set by subpopulations, according to the general methods:

- Dose interruption (number of subjects with at least one interrupted dose, number of infusion interrupted per subject, reason for interruption, total number of interruptions). The dose interruption information will be retrieved from the CRF dosing pages.
- Dose delay (subjects with at least one delayed dose, number of dose delay per subjects, length of delay: 4-7 days, 8-24 days, 25-42 days, and > 42 days, reason for dose delay, total number of dose delays,). A dose will be considered as delayed if the delay is exceeding 3 days (i.e greater than or equal to 4 days from scheduled dosing date).
- Dose infusion rate reduction (number of subjects with at least one infusion with IV rate reduced, number of infusion with IV rate reduced per subject, reason for IV rate reduction, total number of IV rate reduced). The dose infusion rate reduction information will be retrieved from the CRF dosing pages.

A listing will be provided using the all treated analysis set.

7.4.4 Subsequent Therapy

Subsequent therapy will be summarized using the treated analysis set by subpopulations.

- Number of subjects with any subsequent therapy
- Number of subjects who received subsequent radiotherapy
- Number of subjects who received subsequent surgery
- Number of subjects who received subsequent systemic therapy.

7.5 Efficacy

7.5.1 Overall Survival and Overall Response Rate at Week 12

Overall survival is defined as the time between the start of treatment and the date of death due to any cause. A subject who has not died will be censored at last known date alive.

Overall survival will be summarized using Kaplan-Meier (KM) product-limit method and associated statistics in the all treated analysis set by subpopulations. Median values of OS, if estimable, along with 2-sided 95% CI using the Brookmeyer and Crowley method will be calculated. If medians are not estimable, other percentiles (e.g., 10th and 25th) may be reported. OS

rates at selected time points, including survival rates at 6 months, 12 months, 18 months, and 24 months, together with their 95% CIs will also be estimated using KM estimates on the OS curves. Minimum follow-up must be longer than the timepoint of interest to generate the OS rate for that particular timepoint. For example, if the timepoint of interest is 6 months and the interval of enrollment date and last patient last visit is less than 6 months, then, the minimum follow-up is not reached and OS rate is not generated. Associated 2-sided 95% CIs will be calculated using the Greenwood formula.

A swimming plot showing the response, progression, duration of therapy and death will be presented using the all treated analysis set, overall and by ECOG PS 2, Ocular/Uveal, and Mucosal subpopulations only.

The overall response rate is defined as the number of subjects with a complete response (CR) or partial response (PR) at week 12 divided by the number of subjects treated. The overall response will be summarized by binomial response rates and their corresponding two-sided 95% exact CIs using the Clopper-Pearson method. A by subject listing will be provided.

A summary of overall response will also be presented by baseline LDH, BRAF status, and type of autoimmune disorder.

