xv) Patients must have evaluable disease by CT or MRI per RECIST 1.1 criteria (radiographic tumor assessment performed within 6 weeks of first dose of study drug) or clinically apparent disease that the investigator can follow for response.

xvi) Patient Re-enrollment: This study permits the re-enrollment of a subject that has discontinued the study as a pre-treatment failure (ie, subject has not been treated). If re-enrolled, the subject must be re-consented.

b) As of Amendment 03, this criterion is not applicable.

- i) As of Amendment 03, this criterion is not applicable.
- ii) As of Amendment 03, this criterion is not applicable.
 - (1) As of Amendment 03, this criterion is not applicable.
 - (2) As of Amendment 03, this criterion is not applicable.
- iii) As of Amendment 03, this criterion is not applicable.
 - (1) As of Amendment 03, this criterion is not applicable.
 - (2) As of Amendment 03, this criterion is not applicable.
 - (3) As of Amendment 03, this criterion is not applicable.
- iv) As of Amendment 03, this criterion is not applicable.
- v) As of Amendment 03, this criterion is not applicable.
- vi) As of Amendment 03, this criterion is not applicable.
- vii) As of Amendment 03, this criterion is not applicable.
- viii) As of Amendment 03, this criterion is not applicable.
 - (1) As of Amendment 03, this criterion is not applicable.
 - (2) As of Amendment 03, this criterion is not applicable.
 - (3) As of Amendment 03, this criterion is not applicable.
 - (4) As of Amendment 03, this criterion is not applicable.
 - (5) As of Amendment 03, this criterion is not applicable.
 - (a) As of Amendment 03, this criterion is not applicable.
 - (b) As of Amendment 03, this criterion is not applicable.
 - (6) As of Amendment 03, this criterion is not applicable.
 - (7) As of Amendment 03, this criterion is not applicable.
 - (8) As of Amendment 03, this criterion is not applicable.
- ix) As of Amendment 03, this criterion is not applicable.
- x) As of Amendment 03, this criterion is not applicable.
- xi) As of Amendment 03, this criterion is not applicable.

3. Age and Reproductive Status

- a) Men and women, aged ≥ 18 years

- b) Women of childbearing potential (WOCBP) must have a negative serum or urine pregnancy test (minimum sensitivity 25 IU/L or equivalent units of HCG) within 24 hours prior to the start of study drug.
- c) Women must not be breastfeeding

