8.2 Populations for Analyses

- The safety analysis set comprises patients who received at least 1 dose of nivolumab. The analysis of safety, OS, and QoL data will be based on the safety analysis set.
- The response evaluable analysis set comprises patients who received at least 1 dose of nivolumab and have both baseline and at least 1 post-baseline tumor scan.

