8.3.2 Secondary Endpoint(s)

The secondary endpoints include:

- Incidence of all high-grade (Grades 3 and higher), select adverse events
- Median time to onset and median time to resolution (Grades 3-4) of select adverse events
- OS is defined as the time from first dosing date to the date of death. A patient who has not died will be censored at last known date alive. OS will be followed continuously while patients are on treatment and every 3 months via in-person or phone contact after patients discontinue the study drug.

- Investigator-assessed ORR. ORR is defined as the number and percentage of patients with a best overall response (BOR) of confirmed CR or PR. ORR as assessed by the investigator will be reported.

[REDACTED]

[REDACTED]

[REDACTED]

[REDACTED]

[REDACTED]

[REDACTED]

[REDACTED]

[REDACTED]

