8.4 Analyses

The analysis of primary, secondary (excluding ORR), [REDACTED] will be reported for the full safety analysis set and by cohorts based on ECOG PS. ORR will be reported for the response evaluable analysis set and by PS. OS and ORR will be further presented by initial investigator-assessed objective response under treatment with an anti-CTLA-4 monoclonal antibody.

Additional details regarding statistical analyses performed in the study are provided in the Statistical Analysis Plan (SAP), which will be finalized before data base lock.

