2 STUDY DESCRIPTION

2.1 Study Design

The study will include subjects with histologically-confirmed stage III (unresectable) or stage IV advanced melanoma who have documented progression after treatment containing an anti-CTLA-4 monoclonal antibody. Subjects will be treated with 3 mg/kg of nivolumab IV every 2 weeks for a maximum of 24 months. Subjects will undergo screening evaluations to determine eligibility within 6 weeks prior to the first dose following the signing of an informed consent. Each 14-day dosing period will constitute a cycle.

The Scientific Steering Committee will evaluate the clinical risk/benefit ratio closely following a defined Safety Management Plan.

Subjects will undergo screening evaluations to determine eligibility prior to first dose following signed informed consent. Subject's demographic data will be collected: date of birth, gender, disease stage, date of diagnosis, previous treatments, comorbidities, performance status, lactate dehydrogenase (LDH) level, type of melanoma (mucosal, uveal), and mutation status if known (BRAF, NRAS, cKIT).

Safety, including adverse events and physical examination, should be monitored continually, and safety assessments are discussed in Tables 5.1-1 and 5.1-2 of the protocol.

Mandatory initial tumor assessments are to be done at Week 12 (± 7 days). Further tumor assessments should be performed according to institutional standard of care and are recommended every 8 weeks until:

- disease progression
- a concurrent malignancy requires treatment
- the subject is lost to follow up
- the subject withdraws study consent
- completed 24 months of treatment

Subjects will not be permitted to continue their treatment beyond initial Investigator-assessed progressive disease unless they meet the following criteria:

- Investigator-assessed clinical benefit
- Subject is tolerating study drug

The investigator should use his or her clinical judgment to assess clinical benefit by considering whether the subject is clinically deteriorating and unlikely to receive any benefit from continued treatment with nivolumab.

Follow up begins when the decision to discontinue a subject from study therapy is made (no further treatment with nivolumab) and continues up to 5 years from first dose of study therapy until death, withdrawal of study consent, or lost-to-follow-up.

The cohorts are described in Table 1.

Table 1: Subject Cohorts

[figure not shown]
(Cohort Number)	Disease Criteria

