2.4 Protocol Amendments

There are currently 6 approved amendments. Table 2 shows the history of protocol amendments including the dates and change history to the protocol.

Table 2: Protocol Amendments

Document	Date	Summary of Changes
Revised Protocol 05	08-Dec-2015	
 Incorporates Amendment 06
Amendment 06	08-Dec-2015	
 Adds dosing windows to the Time and Events Schedule
Revised Protocol 04	28-Oct-2015	
 Incorporates Administrative Letter 05 and Amendment 05
Amendment 05	28-Oct-2015	
 To provide further clarity on the requirements for lipase testing To provide clarity on dose calculations To allow the EQ-5D-3L to be completed without an office visit if one is not otherwise needed.
Administrative Letter 05	23-Jul-2015	
 The of expectations when lipase results are not available prior to dosing Aligning the footnotes of Table 5.1-2 and Section 5.3, Safety Assessments with the requirements for lipase described in Table 5.1-2. Assessments allowed to be done according to standard of care At what cycle assessments should start and assessment windows When RECIST 1.1 criteria must be used. NOTE: Administrative Letter 04 was not finalized because it was considered to not be needed. However, Administrative Letter 05 was created and finalized with the mistaken understanding that Administrative Letter 04 was finalized.
Revised protocol 03	02-Jun-2015	
 Incorporates Amendment 04
Amendment 04	02-Jun-2015	
 Decreases sample size
Revised Protocol 02	19-Mar-2015	
 Incorporates Amendment 03

Table 2: Protocol Amendments

Document	Date	Summary of Changes
Amendment 03	19-Mar-2015	
 This Amendment removes the inclusion of the treatment-naïve subjects, also referred to as the first-line cohort.
Revised Protocol 01	16-Jan-2015	
 Incorporates Amendment 02 and Administrative Letter 03.

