4.2 Secondary Endpoints

The secondary endpoints include the incidence of all high-grade (Grades 3 and higher) select adverse events, the median time to onset and median time to resolution (Grades 3-4) of select adverse events, the and overall survival (OS) of subjects.

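### SAP 7.5.1 computes CR/PR at Week 12 over all treated patients, which is not the protocol's secondary endpoint of confirmed best overall response in the response-evaluable set

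*SAP*

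**What the plan says.** **Protocol.** Estimating investigator-assessed ORR is a secondary objective (Synopsis) and a secondary endpoint (Section 8.3.2). The definition is: "ORR is defined as the number and percentage of patients with a best overall response (BOR) of confirmed CR or PR". The Synopsis and Section 8.4.3 repeat it. Section 8.4 sets the population: "ORR will be reported for the response evaluable analysis set and by PS". It also asks for ORR by response to the earlier anti-CTLA-4 treatment. Under Section 8.2 the response-evaluable set is limited to patients who were dosed and who "have both baseline and at least 1 post-baseline tumor scan".

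**SAP.** Section 7.5.1 defines the overall response rate as patients with "complete response (CR) or partial response (PR) at week 12 divided by the number of subjects treated", with a Clopper-Pearson interval. It mentions neither best response nor confirmation. SAP 6.3 defines a response-evaluable set like the protocol's, but no readable SAP analysis uses it. SAP 3.2 does not list ORR among the secondary objectives. The endpoint sentence in SAP 4.2 has a gap: "the median time to onset and median time to resolution (Grades 3-4) of select adverse events, the and overall survival (OS) of subjects".

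**Timing of scans.** Week 12 is the only mandatory on-treatment tumor assessment; later scans are recommended every 8 weeks. The Week-12 window is ±5 days in Protocol 3.1, Table 5.1-2 and Section 5.4, but ±7 days in SAP 2.1.

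**The concern.** A programmer working from the SAP would produce a different quantity from the one the protocol names as a secondary endpoint, and the reported ORR would depend on which document was followed.

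- **Numerator.** A Week-12 rule leaves out responses first seen after Week 12, and it can include responses that are never confirmed. These errors pull in opposite directions.
- **Denominator.** The protocol's set drops treated patients without a baseline or post-baseline scan, for example those who die early. If they are non-responders, the protocol's rate is higher than an all-treated rate, and more so in a cohort where early death is more common.

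Because ORR carries no hypothesis test, power calculation or decision rule, the damage is confined to the estimate and its interpretation.

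**Working it through.** The plan states no ORR target or precision, so there is no figure to reproduce. The check has two parts.

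**1. The two definitions side by side**

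| Element | Protocol 8.2, 8.3.2, 8.4 | SAP 7.5.1 |
|---|---|---|
| Response counted | Best overall response | Status at Week 12 |
| Confirmation | Required | Not mentioned |
| Denominator | Dosed, with baseline and post-baseline scan | All treated |
| Split by response to prior anti-CTLA-4 therapy | Yes | Not in the readable text |

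**2. What the differences can do to the number**

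Inputs: 800 treated is the planned maximum (Protocol 8). The rates 20% and 32% are borrowed from Protocol 1.4.1.1 as illustrative all-treated confirmed rates. The share without a post-baseline scan is not given, so a range of 0% to 20% is assumed.

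*Denominator.* With x responders, all scanned, the all-treated rate is x/800 and the evaluable rate is x/(800 − m), where m patients lack a post-baseline scan. Clopper-Pearson 95% intervals are in brackets.

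| Without scan | Evaluable | x = 160 | x = 256 |
|---|---|---|---|
| 0% | 800 | 20.0% (17.3–22.9) | 32.0% (28.8–35.4) |
| 5% | 760 | 21.1% (18.2–24.1) | 33.7% (30.3–37.2) |
| 10% | 720 | 22.2% (19.2–25.4) | 35.6% (32.1–39.2) |
| 20% | 640 | 25.0% (21.7–28.5) | 40.0% (36.2–43.9) |

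If k of the m excluded patients are responders, (x − k)/(n − m) > x/n holds exactly when k/m < x/n. For m = 40 the break-even is 40 × 0.32 = 12.8 or 40 × 0.20 = 8.0. The evaluable rate is therefore higher only with at most 12 excluded responders at 32%, or at most 7 at 20%. With 20 responders among 40 excluded it falls to 236/760 = 31.1% (27.8–34.5), against 32.0%.

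*Numerator.* Over all treated, the Week-12 rate minus the confirmed best-response rate equals the share with a Week-12 response never confirmed, minus the share of confirmed responders not in CR/PR at Week 12. The documents give neither share. Two assumed cases show that the sign is open. Both start from 205 confirmed responders (32% of 640 evaluable, rounded), which is 205/800 = 25.6% over all treated, and both assume unconfirmed responders equal to 20% of the confirmed responders in CR/PR at Week 12:

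- 70% of confirmed responders in CR/PR at Week 12: 144 plus 28 unconfirmed = 172, and 172/800 = 21.5%, below 25.6%.
- 90% in CR/PR at Week 12: 184 plus 37 unconfirmed = 221, and 221/800 = 27.6%, above 25.6%.

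**The case against.** **Redaction and version.** Parts of the SAP are blacked out and SAP 4.2 has a gap, so a protocol-style ORR analysis may exist in text that cannot be read. The unused response-evaluable set and the date rules for progression and last tumor assessment in SAP 8.3 hint at that. The SAP may also be older than the protocol text: it says "There are currently 6 approved amendments" and that follow-up "continues up to 5 years from first dose of study therapy until death", while the protocol cites Amendment 08 and 2 years. This stands as a limit. The finding covers the readable text and does not show that no protocol ORR analysis was ever planned. But the rule in 7.5.1 is fully readable, and a second definition elsewhere would still have to be reconciled with it. An older SAP would explain the mismatch without removing it.

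**The SAP's choices are defensible.** An all-treated denominator is usually conservative, and Week 12 is the one scan everyone should have. Both points are fair, but the SAP gives neither as a reason. The fault is an unexplained change of endpoint.

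**The illustration is weak.** The 20% is 6 of 30 although 33 patients received the sequenced regimen (6/33 = 18.2%). The 32% is a centrally reviewed rate in the first 120 nivolumab-treated patients of another trial. Both cautions are right, and the rates serve only as round starting values.

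**The reversal case is remote.** Eligibility accepts "clinically apparent disease that the investigator can follow for response", but scans are scheduled at baseline and Week 12 for everyone, so excluded responders would have to have missed scheduled scans. That makes a reversal less likely, though not impossible.

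**Conclusion.** The concern holds on the readable text. SAP 7.5.1 differs from the protocol's secondary endpoint in time point, confirmation and denominator, and following it would not estimate that endpoint. It should be fixed.

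The actual size cannot be fixed from the documents. If up to 20% of 800 treated patients lack a post-baseline scan and all responders were scanned, the denominator alone accounts for up to 5 percentage points at a 20% rate and up to 8 at a 32% rate. The direction of the numerator effect is undetermined. No error rate, sample size or decision rule is touched. The ±5 versus ±7 day window is a minor side item, although it matters more if Week 12 defines the endpoint.

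**What to change.** - Add the protocol endpoint to SAP 7.5.1: best overall response of confirmed CR or PR, with a written confirmation rule and assessment period. State the response criteria that apply after Week 12, because Protocol 5.4 names RECIST 1.1 at Week 12 and investigator-assessed response thereafter.
- Report it over all treated, counting patients with no post-baseline response assessment (scan or clinical) as non-responders, with a Clopper-Pearson interval. Beside it, report the response-evaluable version by PS and by response to prior anti-CTLA-4 therapy, as Protocol 8.4 plans.
- Keep the Week-12 CR/PR rate over all treated as a separately labelled result.
- State in both documents which rate is the secondary endpoint.
- Report by PS the number of treated patients with no post-baseline scan and the number of Week-12 responders with a later scan. Scans after Week 12 are only recommended, so confirmation depends partly on local practice.
- Reconcile the two Week-12 windows.

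The cost is wording in the SAP and protocol plus one table, with no new procedures. The all-treated rate will usually be somewhat lower than the response-evaluable rate, and showing both makes the reason visible.
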